varicose veins, atrial fibrillation, history of deep venous thrombosis, heart failure. Moderate-severe comorbidities will be history of myocardial infarction, stroke or transient ischaemic attack, CKD stage 4 or higher, peripheral vascular disease, history of amputation. Any other significant non-vascular conditions will be recorded too (e.g. COPD, cancer, auto-immune disease).

Treatment Deviation outcome data will be collated and presented with descriptive statistics. This will be in the form of the number of treatment deviations that occurred as a result of the WOUNDCHECK test result, the nature of the deviation and the longer term patient/wound outcomes at week 6 and/or week 12.

Ulcer healing and more general health measures is assessed by the following parameters:

- Ulcer status (healed vs non-healed)
- Ulcer size (cm²)
- PUSH score
- SINBAD score
- Visual analogue pain score
- EQ-5D-5L

To assess the Ulcer size, PUSH score, visual analogue pain score, which are measured every 6 weeks, the average difference between groups (ie negative or positive Woundchek test outcome) will be calculated and Mann-Whitney U-test will be applied.

To measure patient-reported outcome measures on quality of life (EQ-5D-5L) at baseline, week6 and week 12; the the Mann-Whitney U-test will be performed between Woundchek test outcome groups.

Analysis will be performed on a per protocol basis, and inferential statistics will be performed on pooled data. Data will first be collated in Microsoft Excel, followed by analyses performed using SPSS v24.

9 Data handling and Monitoring

Data arising from this study is confidential. Identifiable information can only be accessed by delegated members of the study team. Anyone in the research team who will work on Trust premises and see patients, and does not have a substantive contract with NCIC, will need to apply for a letter of access via the NIHR research passport scheme.

Participants will be pseudo anonymised by allocating a study ID to each of them. Patient identifiable data will only be used within North Cumbria Integrated Care NHS Foundation Trust; if applicable, only anonymised data are shared with the wider members of the study team. All identifiable data is stored on password protected NHS computer systems. Anonymised data will be shared and stored using security-enabled systems such as password-protection and encryption of e-mails and files. The requirements of the Data Protection Act and NHS Code of Confidentiality will be followed at all times. All researchers will be fully trained in NHS Confidentiality and GCP.

Participants' GP practices will not be informed that they are taking part in the study.

All paper data will be held in secure locked environments in the office of the Research & Development department in Cumberland Infirmary, Carlisle, North Cumbria Integrated Care NHS Foundation Trust.

Electronic data will be saved on the patient management system such as EMIS, and also a password protected research database. Data released (e.g. by publication) will contain no information that could lead to the identification of an individual participant. Upon completion of the study the site files will be archived for a period of 10 years in line with local archiving policy and procedures.

Direct access to anonymised data only will be granted to authorised representatives from the sponsor, host institution and the regulatory authorities to permit trial-related monitoring, audits and inspections.

Final data, will be shared with WOUNDCHEK™ Ltd in pseudo-anonymised form. The final anonymised dataset will be shared with WOUNDCHEK™ in pseudoanonymised form.

10 Governance of study

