Prospective, single-centre, cohort study assessing the potential application of WOUNDCHEK™ diagnostics for ulcer management

(BIOME, Bacterial Infection: Observation & Management Evaluation)

V1, dd 18 November 2022

Chief Investigator's Statement of Ownership and Content.
I, [name], confirm that this protocol is my work and is owned by me. The protocol conforms to standards outlined in the Declaration of Helsinki 1964.
Name (PRINT):
Signature:
Date:

RESEARCH PROTOCOL SUMMARY

TITLE:	Prospective, single-centre, cohort study assessing the potential application of WOUNDCHEK™ diagnostics for ulcer management
Short title:	BIOME, Bacterial Infection: Observation & Management
	Evaluation
IRAS number	314595
Device description	CE-marked point of care test: WOUNDCHEK™.
	WOUNDCHEK™ Bacterial Status — or WCBS - is able to detect bacterial EPA (elevated protease activity). WOUNDCHEK™ Bacterial Status will help clinicians establish within minutes which wounds may most benefit from a protease modulating therapy, ensuring appropriate and targeted use of these therapies.
Study design	Prospective, single-centre, controlled, non-randomised, prospective cohort comparative study
	Participants' index ulcer will be swabbed twice, at week 0 and at week 6, plus a medium-term assessment at week 12.
Primary objective	Determine if there is a difference in rate of positive outcome between clinical opinion (ie presence of infection based on wound symptoms) and WOUNDCHEK™ Bacterial Status test result for the same wound.
Secondary objectives	To define the degree of concordance between a clinical staff member's opinion and results from the WOUNDCHEK™ detection kit, concerning the assessment of infection presence in ulcer wounds.
	Determine what patient and/or wound characteristic(s) are significantly linked to a non-matching result between clinical opinion and WOUNDCHEK™ WCBS result. These outcomes are relevant for application of the WOUNDCHEK™ test in standard clinical practice. Two binary logistic regression analyses will be conducted for variables associated with the sample's proportion of non-matched outcome: - Clinical opinion negative ('no infection') vs WOUNDCHEK™ test positive or - Clinical opinion positive ('possible' or 'definite' infection) vs WOUNDCHEK™ test negative

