	Evaluate if there are factors associated with infection rates and/or WOUNDCHEK™ result, including clinical indicators of infection such as erythema, purulence, odour, and patient characteristics (health status, co-morbidities, demographic).
	Assess if there are any trends in bacterial protease detection rates in ulcers when patients are followed up, ie result of first test versus second follow-up test of same ulcer
	Evaluate if clinical staff deviate from their initial treatment plan once the WOUNDCHEK result is available to them during a consultation

	T
Inclusion & Exclusion	Inclusion criteria:
criteria	- Adult patients aged ≥ 18 years
	- Patients can be newly presenting to or existing users of the
	specialist service in question (eg podiatry, vascular surgery)
	- Patients with recurrent wounds, including multiple wounds, are
	eligible; largest ulcer to be index wound - If infection occurs and antibiotics applied, whilst in study, then
	this is not deemed an exclusion criterion.
	 Prophylactic systemic antibiotic use is not an exclusion criterion
	- Chronicity: clinical diagnosis of ulcer with wound duration > 30
	days.
	- Wound type:
	 Leg ulcer (can be venous, mixed or arterial in nature)
	 Foot ulcer (can be diabetic or non-diabetic in nature)
	Exclusion criteria:
	- Aged < 18 years
	- Any reasons for the patient being unable to follow the protocol,
	including lack of mental capacity to consent to taking part in the
	study.
	- The patient has concurrent (medical) conditions that in the
	opinion of the investigator may compromise patient safety or
	study objectives
	- Confirmed and ongoing wound infection at baseline which is
	already being treated with systemic antibiotics (within 3 weeks
	of first study visit) Previous participation in BIOME study
	- Trevious participation in biolivic study
Sample size	258 samples required, taken from minimum of 129 patients at week0
	and week6 visits. This study element is powered to detect a 4%
	difference in detection of clinician-specified wound infection and a
	positive WOUNDCHEK™ Bacterial Status test result. (Chi-squared test,
	80% power, p-value 0.05, 10% attrition rate). This is provided the
	incidence of infection detected equals 9% and 5% per rater,
	respectively.
	Furthermore, the study is also sufficiently powered to detect an inter-
	rater concordance level (Kappa) of 0.9, at 80% power and an infection detection rate of 10%.
	detection rate of 10%.
Manufacturer & provider	WOUNDCHEK™ Laboratories

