Chronic ulcer wounds of the legs and feet can be challenging for healthcare staff to manage. Patients often have co-morbidities and there is a considerable likelihood of non-healing and recurrence of ulcers, plus infection can occur. Apart from having a significant negative impact on patients' lives, it is also a huge economic burden to the National Health Service. Clinical opinion — by checking for hallmark signs of infection - is the main way to determine if a wound is infected. Microbiology testing offers information on what type of antibiotic may help to treat the infection. Different companies have developed point-of-care tests that assess something that cannot be readily observed: bacterial protease activity. Its presence may be indicative of infection since bacteria use said protease enzymes to break down protein structures in a wound that are needed for a wound to heal. Due to logistic and cost reasons it would not be practical to apply a protease point-of-care test for all patients' wounds. This study investigates to what degree clinical opinion and results of the WOUNDCHEK Bacterial Status test align, and also what factors and variables may be associated with non-matching results. Furthermore, the degree of influence the WOUNCHEK test result may have on clinical management of chronic lower limb ulcers will be explored. For this purpose a total of 258 wounds (minimum of 129 patients) will be assessed at baseline and then six and twelve weeks later.

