5.2 STUDY PROCEDURES

Initial assessments at visit 1 (week 0)

After completing informed consent, the nature of the patient's wound will be recorded as well as the other relevant clinical parameters and demographics. The first WOUNDCHEK™ test will also be conducted. See Table 3 for an overview. Dressing selection, dressing frequency and all other aspects of their wound care will continue to be the responsibility of the clinical team – however, if they are influenced in this decision by the result of the WOUNDCHEK™ test then they are asked to record this in the clinical report form.

All visit assessments

Study visits will coincide with standard clinic attendance by patients. At the study visits week0 and week6, a diagnostic swab using the WOUNDCHEK™ infection detection test kit is performed in accordance with the SOP in Appendix 5.

The clinical staff treating the patient will ascertain their opinion regarding infection status of the wound prior to completing the WOUNDCHEK™ detection test, and will therefore be blinded to at least the first result of using the kit. Where possible, a member of the research team plus the clinical assessor will assess result of the WOUNDCHEK™ test.

Table 4, Overview of study activities per time point for different study participants.

Weeks	Visit 1 (wk 0)	Visit 2 (wk 6)#	Visit 3 (wk 12)#
Treatment deviation question	X	Χ	
WOUNDCHEK™ test (method, see appendix 6)	Χ	Χ	
Wound healed status~	n/a	X (if healed, no other	X (if healed, no other
		outcome measures)	outcome measures)
Clinical opinion of ulcer re. infection	Χ	Χ	Χ
PUSH score ulcer size (appendix 3)	X	Χ	Χ
VAS pain scale (appendix 3)	Χ	Χ	Χ
SINBAD score (foot ulcers only, appendix 4)	X	Χ	X
QoL EQ-5D-5L (appendix 5)	Χ	Χ	Χ
Wound measurement*(if standard care	X	Χ	Х
activity)			

[~]Wound status (healed vs non-healed), definition is: complete epithelial cover in the absence of a scab (eschar) with no dressing required bar any protective dressing. There is no minimum length of time that the index site has to have been in said condition for when participant present for follow-up study visit. # Can be \pm two weeks.

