8.2 SAMPLE SIZE CALCULATION

The primary outcome, presence of bacterial infection is used for sample size calculation. Data from studies involving another point-of-care test (Jonker et al, 2020 and Jonker et al 2022) gives some guidance on the incidence of wound infection as defined by clinical staff. Circa 5% of samples were deemed as infected by clinical staff. A hypothetical difference in opinion/outcome of 4% is used to determine the required sample size that has sufficient power to detect such a difference.

Power calculations for sample size, 80% power and 5% significance, based on two-sided Chi-squared test. A priori power calculations using GPower 3.1 software, result in the following sample size summarized in Table 6. The raters are the WOUNDCHEK WCBC and the clinical staff. Patients will be recruited from the adult (age 18+) population routinely seen by the evaluating clinical staff members. Attrition rate — determined in other similar studies — is anticipated to be 10%.

Table 6, Sample size calculation for BIOME study

	No infection	Infection		
Rater A (hypothetical)	0.95	0.05		
Rater B (hypothetical)	0.91	0.09		
	Power beta of 80%, Alpha p-value o size 0.184	ample size required without any attrition: 234 samples. Emple size required with 10% attrition: 258 samples		
	week 0 and week 6 (258 sar attend twice, eg due to a we			

The above sample size will also allow to assess the secondary objective, ie concordance between the two raters – namely clinical opinion and WOUNDCHEK™ test result - at a confidence level of 90% and Kappa concordance level of 0.80 (calculated via https://wnarifin.github.io/ssc/sskappa.html).

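### Week-0 and week-6 results from the same ulcer are counted and pooled as separate observations, with no allowance for two results per patient

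*Protocol*

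**What the plan says.** The protocol summary sets out the sampling under study design: "Participants' index ulcer will be swabbed twice, at week 0 and at week 6, plus a medium-term assessment at week 12". The sample size entry in the same summary reads "258 samples required, taken from minimum of 129 patients at week0", and continues to the week-6 visit. The unit counted is therefore the swab, with up to two per patient.

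Section 8.2 bases the number on a chi-squared calculation: "Power calculations for sample size, 80% power and 5% significance, based on two-sided Chi-squared test". The summary gives the assumed rates as "incidence of infection detected equals 9% and 5% per rater", and Table 6 gives the sample "size required without any attrition: 234 samples", raised to 258 for 10% attrition.

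Section 8.3 names the chi-squared test on the cross-tabulation as primary, together with kappa. Section 8.4 adds binary logistic regressions and closes with "Analysis will be performed on a per protocol basis, and inferential statistics will be performed on pooled data".

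On blinding, Section 5.2 has staff record their opinion before completing the test, so that they "will therefore be blinded to at least the first result of using the kit".

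The lay summary before Section 1 describes the count differently: "a total of 258 wounds (minimum of 129 patients) will be assessed at baseline and then six and twelve weeks later".

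**The concern.** Two results from one ulcer six weeks apart are repeated measures. The protocol treats them as such in Section 2.2, where comparing the first with the second test of the same ulcer is a secondary objective. The methods named for the main comparisons, in their ordinary form, take every row as independent. Age, sex, co-morbidity and wound type would enter the regressions twice for each patient with two swabs. At stake are the p-values and intervals for pooled rates, kappa and patient-level factors, and the claim of 80% power.

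There is a second, smaller point. Pooling combines a round in which the opinion is blind to any test result with a round in which staff may already know the week-0 result for that ulcer. Sections 2.2 and 3.1 make clear that staff see the result during the consultation and may act on it.

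**Working it through.** **Inputs from the protocol.** Rates 5% and 9%; two-sided alpha 0.05; power 80%; effect size 0.184; 234 samples before attrition and 258 after; attrition 10%; up to m = 2 swabs per ulcer.

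**Input not in the protocol.** The within-ulcer correlation of week-0 and week-6 results, rho. Assumed values: 0.1, 0.2, 0.3, 0.5.

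**Step 1: reproduce the plan's figure.** For a one-degree-of-freedom chi-squared test of 9% against 5%:

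w = sqrt(0.04²/0.95 + 0.04²/0.05) = sqrt(0.00168 + 0.03200) = 0.1835.

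The noncentral chi-squared distribution with noncentrality N·w² first reaches 80% power at N = 234, which matches Table 6. Attrition: 234 × 1.10 = 257.4, rounded up to 258. In this formula every sample is one independent observation, so no allowance for repeated swabs is hidden in the 234.

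**Step 2: allow for two swabs per ulcer.**

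- Design effect: DE = 1 + (m − 1)·rho = 1 + rho
- Effective number: 234/DE
- Factor by which the true standard error exceeds the naive one: sqrt(DE)
- True two-sided error of a nominal 5% test: 2·[1 − Φ(1.96/sqrt(DE))]
- Power with a correct variance: as in step 1, with N = 234/DE
- Samples needed before attrition: 234·DE, rounded up

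| rho | DE | Effective n of 234 | SE factor | True error | Power, 234 | Power, 258 | Samples needed |
|---|---|---|---|---|---|---|---|
| 0 | 1.0 | 234 | 1.00 | 5.0% | 80% | 84% | 234 |
| 0.1 | 1.1 | 213 | 1.05 | 6.2% | 76% | 80% | 258 |
| 0.2 | 1.2 | 195 | 1.10 | 7.4% | 73% | 77% | 281 |
| 0.3 | 1.3 | 180 | 1.14 | 8.6% | 69% | 73% | 305 |
| 0.5 | 1.5 | 156 | 1.22 | 11.0% | 63% | 67% | 351 |

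A simulation of 117 patients with two results each and a true rate of 5% gave error rates of 6.4%, 8.0% and 10.7% at rho 0.1, 0.3 and 0.5, close to the formula.

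**Step 3: limits of the table.** Under Sections 5.2 and 5.3 a healed ulcer gives no week-6 swab, so the mean number of swabs per patient is below 2 and DE is below 1 + rho. Each row is an upper-end figure for its rho. The rows apply to a pooled proportion and, by the same logic, to covariates that are constant within a patient.

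**Step 4: blinding.** Sections 3.2 and 5.2 and the form in Appendix 1 place the opinion before the test at each visit, so week 0 is clean. At week 6 the same-day result is still unknown, but the week-0 result has been disclosed. Section 5.2 claims blinding for the first result only as a minimum, and nothing requires a different or unaware assessor at week 6.

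**The case against.** The sentence on pooling does not say what is pooled. It could mean clinics or wound types, and the protocol nowhere calls the results independent. This is fair as far as that sentence goes. However, the 258 already adds both visits together, the formula that returns 234 has no term for repeated swabs, and none of the named methods is clustered or run by visit for these comparisons. An analysis plan could add a clustered method, but the protocol itself fixes the count, the tests and the pooling.

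Three stronger readings are tempting, and the document does not support them.

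- **That pooled agreement is inflated.** Only a six-week-old result can be known at week 6, and only if the same clinician returns or the record is consulted. Section 2.2 lists the clinical rater as a factor, so raters may differ. Treatment changed after week 0 alters the wound that both the clinician and the test then assess. An effect is possible; its direction is not established.
- **That all covariate effects have standard errors that are too small.** Erythema, purulence, odour, pain, wound size and quality of life are recorded afresh at each visit. For these the error can go either way.
- **That the error rates in the table apply directly to the difference between opinion and test.** Both are read on the same ulcer at the same visit. The relevant correlation is that of the opinion-minus-test difference between visits, which may be lower.

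**Conclusion.** The point holds. As written, the plan counts and analyses up to two results per patient as separate observations. With any positive within-ulcer correlation, standard errors are too small for pooled proportions, kappa and patient-level covariates, and the protocol's own test falls short of 80% power on its 234 analysed samples. Across rho 0.1 to 0.5, true error is about 6.2% to 11.0% and power about 76% to 63%. The size rests on an assumed rho and on two swabs from every patient, so it is a range and not an estimate.

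The week-6 blinding gap is a reason to show week 0 separately. It is not evidence of bias in a known direction.

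The count of 258 wounds in the lay summary conflicts with the samples counted in the protocol summary and Section 8.2.

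**What to change.** - In Section 8.4, replace the pooling rule with analyses that cluster on patient: GEE with robust standard errors and a visit term, for the opinion-versus-test rate difference and for each logistic regression. Align the primary test in Section 8.3 with this.
- Obtain the kappa interval by bootstrap, resampling patients and not swabs.
- Report the week-0 rate difference and kappa separately as the fully blinded estimate, beside the two-visit estimate. Clustering corrects the variance; it does not remove any effect of knowing the earlier result.
- In Section 8.2, restate power over a stated range of within-ulcer correlations, allowing for ulcers that give one swab only.
- In the lay summary, change the count to 258 samples from a minimum of 129 patients. The word minimum must stay, because patients with a single swab push the number of patients above 129.

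**Cost.** No extra visits or swabs are needed to correct the analysis, and GEE is feasible in the planned SPSS. The price is wider intervals, a less favourable stated power, a changed primary test that needs an amendment, and a week-0 estimate on about half the samples. If 80% power is to be kept, the number must rise: at rho 0.3, to 305 samples before attrition instead of 234.

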10.1 APPROVALS

This study will be conducted in compliance with the protocol approved by the Health Research Authority, National Research Ethics Service, and local Trust R&D Approval, and according to Good Clinical Practice standards including the Declaration of Helsinki (1964, Amended Oct 2013). No deviation from the protocol will be implemented without the prior review and approval of the aforementioned review bodies, except where it may be necessary to eliminate an immediate hazard to a research subject. In such case, the deviation will be reported according to policies and procedures.

Patient on oral/iv non-prophylactic antibiotics within 3 weeks (week0) or since last study visit (week6/12)? (yes/no)	If yes, patient not eligible!		
Oral/iv non-prophylactic antibiotics prescribed at this clinic visit? (yes/no)			
Swab sent for microbiology testing? (yes / no)			
Was wound debridement carried out? (yes / no)			
PUSH wound size score completed (yes / no)			
Patient VAS pain score completed (yes / no)			
QoL EQ-5D-5L completed (yes / no)			

PLEASE TURN OV	ER SHEET FOR MORE QUE	STIONS
Patient visit #	1 (study week 0)	2 (study week 6)
Any treatment deviation as a result of WOUNDCHEK result?	YES / NO	YES / NO
If YES to above question	Wound dressing	Wound dressing

Appendix 2, Study participant flowchart

Appendix 3, PUSH score and VAS pain scale

The Pressure Ulcer Scale for Healing (PUSH) tool is a standardised method of assessing and monitoring the severity and healing of both pressure ulcers and venous leg ulcers (Stotts et al, 2001; Ratliff & Rodeheaver 2005). The Pressure Ulcer Scale for Healing (PUSH) is a valid, responsive, evaluative tool to monitor and document wound progress of foot ulcers (Hon, 2010).

Pressure Ulcer Scale for Healing (PUSH) PUSH Tool 3.0

[figure not shown]
Patient Name	Patient ID#	
Ulcer Location	Date	

Directions:

Observe and measure the pressure ulcer. Categorize the ulcer with respect to surface area, exudate, and type of wound tissue. Record a sub-score for each of these ulcer characteristics. Add the sub-scores to obtain the total score. A comparison of total scores measured over time provides an indication of the improvement or deterioration in pressure ulcer healing.

LENGTH	0	1	2	3	4	5	Sub-score
X	0	< 0.3	0.3 – 0.6	0.7 – 1.0	1.1 – 2.0	2.1 – 3.0	
		6	7	8	9	10	
(in cm²)		3.1 – 4.0	4.1 – 8.0	8.1 – 12.0	12.1 - 24.0	> 24.0	
EXUDATE	0	1	2	3			Sub-score
AMOUNT	None	Light	Moderate	Heavy			
TISSUE	0	1	2	3	4		Sub-score
TYPE	Closed	Epithelial Tissue	Granulation Tissue	Slough	Necrotic Tissue		
			1				TOTAL SCORE

Visual analogue pain scale, for pain currently experienced from site of wound (enter in table, not on the scale itself):

